3. ENDPOINTS AND BASELINE VARIABLES: DEFINITIONS AND CONVENTIONS

3.1. Primary Endpoint(s)

- Local reactions (pain at the injection site, redness, and swelling) through 7 days following vaccination.
- Systemic events (fever, fatigue, headache, chills, vomiting, diarrhea, new or worsened muscle pain, and new or worsened joint pain) through 7 days following vaccination.
- AEs through 4 weeks after vaccination.
- SAEs through 6 months after vaccination.
- MAEs through 6 months after vaccination.
- NDCMCs through 6 months after vaccination.

3.1.1. Local Reactions

The local reactions reported in the e-diary are pain at the injection site, redness, and swelling, from Day 1 through Day 7 after vaccination, where Day 1 is the day of vaccination.

If a local reaction persists beyond the end of the 7-day e-diary collection period following vaccination, the participant will be requested to report that information and the corresponding resolution date. The investigator will enter this resolution date on the Summary of Reactogenicity CRF page.

For missing records on local reactions during the 7-day e-diary collection period, the data may be retrieved by the investigator via participant report and collected in the CRF. The local reactions collected on the Participant Reported Reactogenicity CRF page will be combined with the 7-day e-diary data and included for the below analysis (presence, maximum severity, onset day, and duration). The main reason for missing e-diary entries (missing when all reactogenicity entries are considered, including any recalled e-diary entries and data entered on the Participant Reported Reactogenicity CRF page) will be collected by the investigator on the Summary of Reactogenicity CRF page.

This section describes derivations with details for the assessment of local reactions: any presence, maximum severity, duration, and onset day of local reactions, in addition to any presence of severe local reactions.

Presence or Absence

For the data summary of the presence (yes or no) of a local reaction during the interval from Day 1 through Day 7 after vaccination, where Day 1 is the day of vaccination, the following variables are required in order to compute the proportions:

- Presence (yes or no) of each severe/Grade 4 local reaction on each day and any day (Day 1 through Day 7).
- Presence (yes or no) of each local reaction by maximum severity on any day (Day 1 through Day 7).

For each local reaction and any local reaction on any day, [Table 3](#) and [Table 4](#) details the algorithm to derive the presence of a reaction (yes or no) during the interval from Day 1 through Day 7, where Day 1 is the day of vaccination.

Table 3. Derived Variables for Presence of Each Local Reaction Within 7 Days After Vaccination

Variable ^a	Yes (1)	No (0)	Missing (.) ^b
Presence of each local reaction.	Participant reports the reaction as “yes” on any day (Day 1 through Day 7)	Participant reports the reaction as “no” or “I don’t recall” on all 7 days (Day 1 through Day 7) or as a combination of “no,” “I don’t recall,” and missing on all 7 days (Day 1 through Day 7).	Participant does not report any data on all 7 days (Day 1 through Day 7) for the reaction.

- a. The variables will be derived for each of the local reactions (redness, swelling, and pain at the injection site) and for each of the severe local reactions within the interval from Day 1 through Day 7 after vaccination.
- b. "Missing" means missing from both the e-diary and the Participant Reported Reactogenicity CRF page.

Table 4. Derived Variables for Presence of Any Local Reaction Within 7 Days After Vaccination

Variable ^a	Yes (1)	No (0)	Missing (.) ^b
Presence of any local reaction.	Participant reports any local reaction as “yes” on any day (Day 1 through Day 7).	For all 3 local reactions, participant reports “no” or “I don’t recall” on all 7 days (Day 1 through Day 7) or as a combination of “no,” “I don’t recall,” and missing on all 7 days (Day 1 through Day 7).	Participant does not report any data for all 3 local reactions on all 7 days (Day 1 through Day 7).

- a. The variables will be derived for any of the local reactions (redness, swelling, and pain at the injection site) and for any of the severe local reactions within the interval from Day 1 through Day 7 after vaccination.
- b. "Missing" means missing from both the e-diary and the Participant Reported Reactogenicity CRF page.

Severity and Maximum Severity

Redness and swelling will be measured and recorded in measuring device units (range: 1 to 21) and then categorized during analysis as absent, mild, moderate, or severe based on the grading scale in [Table 5](#). Measuring device units can be converted to centimeters according to the following formula: 1 measuring device unit = 0.5 cm. Pain at the injection site will be assessed by the participant as absent, mild, moderate, or severe according to the grading scale in [Table 5](#).

Table 5. Local Reaction Grading Scale

	Mild (Grade 1)	Moderate (Grade 2)	Severe (Grade 3)	Potentially Life-Threatening (Grade 4^a)
Pain at the injection site	Does not interfere with activity	Interferes with activity	Prevents daily activity	Emergency room visit or hospitalization for severe pain
Redness	>2.0 cm to 5.0 cm (5 to 10 measuring device units)	>5.0 cm to 10.0 cm (11 to 20 measuring device units)	>10 cm (≥21 measuring device units)	Necrosis or exfoliative dermatitis
Swelling	>2.0 cm to 5.0 cm (5 to 10 measuring device units)	>5.0 cm to 10.0 cm (11 to 20 measuring device units)	>10 cm (≥21 measuring device units)	Necrosis

- a. Only an investigator or qualified designee is able to classify a participant's local reaction as Grade 4, after clinical evaluation of the participant or documentation from another medically qualified source (eg, emergency room or hospital record) or telephone contact with the participant. A Grade 4 reaction that meets the definition of an SAE will be collected on the AE CRF.

For each local reaction reported, the maximum severity grade will be derived for the e-diary collection period (Day 1 through Day 7, where Day 1 is the day of vaccination) as follows:

Maximum severity grade = highest grade (maximum severity) within 7 days after vaccination (Day 1 through Day 7) among severity grades where the answers are neither “no” nor missing for at least 1 day during the interval from Day 1 through Day 7.

Duration of Each Local Reaction (First to Last Day Reported)

For participants experiencing any local reaction (or those with a derived reaction as described in [Table 3](#) and [Table 4](#)), the maximum duration (resolution date of reaction – start date of reaction + 1) will be derived for each study vaccination.

Resolution of the reaction is the last day on which the reaction is recorded in the e-diary or the date the reaction ends if it is unresolved during the participant e-diary recording period (end date collected in the CRF), unless chronicity is established. If there is no known end date, the duration will be considered unknown and set to “missing.” Participants with no reported reactions have no duration.

Onset Day of Each Local Reaction

The onset day of each local reaction will be derived. Onset day is defined as the first day of reporting any severity.

For the onset day of each local reaction, only the first day of reporting that specific local reaction will be counted, even if participants report a change in severity of the local reaction.

In summary, the following variables will be derived for local reactions:

1. Presence or absence of each local reaction on each day (Day 1 through Day 7) after vaccination.
2. Presence or absence of each local reaction on any day (Day 1 through Day 7) after vaccination.
3. Presence or absence of each severe/Grade 4 local reaction on each day and any day (Day 1 through Day 7) after vaccination.
4. Maximum severity of each local reaction on any day (Day 1 through Day 7) after vaccination.
5. Presence or absence of any local reaction on any day (Day 1 through Day 7) after vaccination.
6. Duration of each local reaction after vaccination.
7. Onset day of each local reaction after vaccination.
8. Onset day of any local reaction after vaccination.

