#### **8.3.4. Reactogenicity Electronic Diary**

Participants will be required to complete a reactogenicity e-diary through an application installed on a provisioned device or on the participant's own personal device. Participants will be asked to monitor prespecified local reactions and systemic events daily for 7 days, or longer for ongoing events after study vaccination, where Day 1 is the day of vaccination until symptom resolution.

The reactogenicity e-diary allows recording of these assessments each day, thus providing the accurate representation of the participant's experience. Data on local reactions and systemic events reported in the reactogenicity e-diary will be transferred electronically to a third-party vendor, where they will be available for review by investigators and the Pfizer clinicians at all times via an internet-based portal.

At intervals agreed to by the vendor and Pfizer, these data will be transferred electronically into Pfizer's database for analysis and reporting. These data do not need to be reported by the investigator in the CRF.

Investigators (or a designee) will be required to review the reactogenicity e-diary data online at frequent intervals as part of the ongoing safety review.

If a participant withdraws because of prespecified event(s) recorded in the e-diary, the event(s) should be recorded on the CRF, regardless of whether the investigator considers the event(s) to be clinically significant.

The investigator or designee must obtain stop dates for any symptoms ongoing on the last day the e-diary is completed until resolution. The stop dates should be documented in the source documents and the information entered in the CRF.

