5.3.1.1. Reactogenicity Data

Completely missing reactogenicity e-diary data (no data from both the 7-day e-diary and the Participant Reported Reactogenicity CRF page) will not be imputed. For derived variables based on reactogenicity data, if any day of the 7-day e-diary data are available, the “any day (Day 1 through Day 7)” data will be considered nonmissing.

The reactogenicity data are collected through the e-diary, which does not allow participants to skip the question. Therefore, for a specific day, as long as the e-diary data are transferred for that day, all of the reactogenicity data for the participant on that day are nonmissing.

For the “I do not recall” data in the e-diary, it will be imputed as “no” as described in [Table 3](#) and [Table 4 in Section 3.1.1](#). No missing reactogenicity data will be imputed other than what is described in [Section 3.1.1](#) and [Section 3.1.2](#).

In summary, for any participant with all 7 days of the e-diary missing (no data from both the 7-day e-diary collection period and the Participant Reported Reactogenicity CRF page), this will not be included in the analysis (ie, assuming MCAR). If only 1 to 6 days of reactogenicity data are available, the reactogenicity data for the missing day(s) are considered as answering “no” for all reactions. This is based on the common assumption that no reports mean no events. See [Table 3](#) and [Table 4](#) for the derivation algorithms.

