6.1.1.2. Sensitivity/Supplementary Analyses

A sensitivity analysis will be conducted for the above summary of reactogenicity events by maximum severity. A variable to indicate the time period from the planned e-diary day (11:59 PM on that calendar day) to the actual time of e-diary reporting will be derived based on FARFTDTC (reference time point, ie, the time of vaccination), FADTC (data collection time), and FATPT (time point of intended solicitation day) in the dataset. The period will be categorized in relation to the planned e-diary day, ie, within the planned day, 1 day out (1-24 hours), 2 days out (>24-48 hours), or 3 days out (>48-72 hours) from the planned e-diary day. The sensitivity analysis will exclude the participants with e-diary reports collected outside the intended solicitation (calendar) day or with data collected from the Participant Reported Reactogenicity CRF page.

To support the assessment of reactogenicity, the endpoints below, as specified in [Section 3.1.1](#) and [Section 3.1.2](#), will be summarized with the same analysis time point and analysis population:

- Duration (days) of each local reaction and each systemic event after vaccination.
- Onset day of each local reaction and each systemic event after vaccination.
- Presence of each and any severe local reaction and each and any severe systemic event on each of the 7 days and for “any day (Day 1 through Day 7).”

The presentation of the results will include a basic descriptive summary without 95% CIs ([Section 5.2](#)).

These continuous endpoints will be summarized by displaying the n, mean, median, standard deviation, minimum, and maximum for each study intervention group.

In addition, the proportions of participants reporting prompted local reactions, by maximum severity level, with any e-diary errors will be included as a supplemental summary.

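### Reactions still present after Day 7 with no recorded end date, and chronic ones, have no duration value and leave the duration summary, so its mean and maximum can be understated

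*SAP*

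**What the plan says.** The Substudy A, B and C SAPs carry the same text.

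- **Formula (3.1.1).** For a participant with a reaction, "the maximum duration (resolution date of reaction – start date of reaction + 1) will be derived for each study vaccination".
- **Resolution (3.1.1).** "Resolution of the reaction is the last day on which the reaction is recorded in the e-diary or the date the reaction ends", the second alternative applying when the reaction is unresolved during the diary recording period and the end date comes from the CRF. The sentence closes with an exception, "unless chronicity is established", but no value is assigned to a chronic reaction.
- **No end date (3.1.1).** "If there is no known end date, the duration will be considered unknown and set to" missing.
- **Systemic events (3.1.2).** Handled in the same manner as local reactions, duration included.
- **Imputation (5.3.1.1).** "No missing reactogenicity data will be imputed other than what is described in" Sections 3.1.1 and 3.1.2, so a missing duration stays missing.
- **Reporting (6.1.1.2).** The supporting summaries include "Duration (days) of each local reaction and each systemic event after vaccination". "These continuous endpoints will be summarized by displaying the n, mean, median, standard deviation, minimum, and maximum for each study intervention group". The only sensitivity analysis in that section concerns maximum severity and late or CRF-retrieved diary data, not duration.

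Two provisions limit how often an end date is absent. Protocol 8.3.4 says "The investigator or designee must obtain stop dates for any symptoms ongoing on the last day the e-diary is completed until resolution", and the 4-week visit procedures (for Substudy A, Protocol 10.11.8.10.2) have the site follow ongoing reactions until they resolve. SAP 2.3 keeps e-diary entries going after Day 7 for participants with ongoing symptoms, to track how long they last.

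**The concern.** A reaction that outlasts contact with the participant is right-censored: its exact length is unknown, but it lasted at least until the last day it was known to be present. Setting it to missing discards that minimum. The loss is also selective, because a long reaction has more opportunity to be cut off by withdrawal or loss to follow-up, and a chronic one has no end to record. The duration table then describes mainly reactions seen to resolve.

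Duration supports the primary tolerability objective, and it is the only specified numerical summary of how long prompted reactions persist beyond Day 7. The understatement would be greatest in a group with more persistent reactions, which is where the table is most needed. In the duration table alone, a group with one unresolved reaction could show the same maximum as a group with none.

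**Working it through.** The documents give no duration, no rate of unresolved reactions and no rate of absent end dates, so there is no planned figure to reproduce. The inputs below are assumptions, except the group sizes (about 90 in Substudies A and B, about 30 in Substudy C; Protocol 10.11.9.5, 10.12.9.5 and 10.13.9.5).

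**1. How likely is at least one case in a group?** If a proportion p of participants has a reaction with no end date, the chance is 1 − (1 − p)^n.

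| assumed p | n = 90 | n = 30 |
|---|---|---|
| 0.5% | 36.3% | 14.0% |
| 1% | 59.5% | 26.0% |
| 2% | 83.8% | 45.5% |

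These match the corresponding rows of Protocol Tables 6, 8 and 11, which use the same formula for AEs. They do not say what p is.

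**2. What does one case do to the summary?** Assume onset on Day 1, so a reaction last known present on Day D has lasted at least D days.

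*54 reactors, 53 resolved.* Assumed resolved durations: 16 of 1 day, 15 of 2, 11 of 3, 6 of 4, 3 of 5, 1 of 6 and 1 of 7. They sum to 131 days.
- SAP rule: 131/53 = 2.47 days, maximum 7.
- Keeping the 54th reactor at the lower bound: (131 + D)/54.

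*20 reactors, 19 resolved.* Assumed resolved durations: 6 of 1 day, 6 of 2, 4 of 3, 2 of 4 and 1 of 5. They sum to 43 days.
- SAP rule: 43/19 = 2.26 days, maximum 5.
- Keeping the 20th reactor at the lower bound: (43 + D)/20.

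| Last known present | 54 reactors: mean (shift) | 54: maximum | 20 reactors: mean (shift) | 20: maximum |
|---|---|---|---|---|
| Day 8 | 139/54 = 2.57 (+0.10) | ≥8 | 51/20 = 2.55 (+0.29) | ≥8 |
| Day 14 | 145/54 = 2.69 (+0.21) | ≥14 | 57/20 = 2.85 (+0.59) | ≥14 |
| Day 28 | 159/54 = 2.94 (+0.47) | ≥28 | 71/20 = 3.55 (+1.29) | ≥28 |

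The median is 2 days under either handling in every row, and so is the Kaplan-Meier median.

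**3. More than one case.** With 3 of 54 unresolved, the 51 resolved durations sum to 124, and the SAP rule gives 124/51 = 2.43. Keeping the three at D = 8, 14 or 28 gives 148/54 = 2.74, 166/54 = 3.07 or 208/54 = 3.85.

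**4. Leaving during Days 1–7 while symptomatic.** The text has two readings. If resolution is the last diary day with the reaction, and missing diary days count as no (5.3.1.1), a participant with onset on Day 1 and a last entry on Day 3 is kept at 3 − 1 + 1 = 3 days, as if resolved. If the reaction counts as unresolved with no CRF end date, the duration is missing. The first truncates the reaction and the second removes it.

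**The case against.** The plan works to prevent the missing state. Stop dates are mandatory to resolution, sites follow ongoing reactions past the 4-week visit, and a reaction beyond Day 7 with an end date keeps its full length. What remains is a chronic reaction, or a participant lost or withdrawing consent while symptomatic. This stands, and is why the effect is probably small.

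A reader might infer that reactogenicity withdrawals are hidden. The documents do not support that. Protocol 8.3.4 requires an e-diary event that causes withdrawal to be recorded on the CRF, SAP 6.1.2.2 summarises AEs leading to withdrawal, and SAP 6.6.2.1 tabulates reasons for withdrawal by group. Nor is duration the only view of persistence: severe reactions are shown for each of Days 1 to 7, and data from the Summary of Reactogenicity CRF page are to be summarised or listed (6.3.1). The displayed n also reveals part of the loss. None of these requires the number of unresolved reactions, or their known minimum length, to be reported.

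A reader might also infer that everyone who leaves while symptomatic drops out. That is too broad: someone leaving during Days 1–7 may instead be kept with a truncated duration. Nor is it right that the absence of an end date is always caused by the length of the reaction. Loss to follow-up can be unrelated; long reactions are only more exposed to it.

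Finally, duration is a supplementary summary without confidence intervals, in substudies with no hypotheses or decision rules. That limits the consequence but does not make the rule a good one.

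**Conclusion.** The point holds in limited form. The clear case is a reaction continuing past Day 7 with no recorded end date, or one judged chronic: it has no duration value and leaves the summary, so the mean and maximum can be understated.

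The size cannot be fixed from the documents. The illustrated shifts rest on an assumed duration distribution, onset on Day 1, and one case last known symptomatic between Day 8 and Day 28. The change in the maximum is the more robust result, since any single unresolved reaction longer than the longest resolved one alters it. A general statement that reported durations are biased short goes too far, because the median is barely affected and a group with complete stop dates is not affected at all. This is a worthwhile small improvement, not a threat to the primary analysis.

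**What to change.** In Sections 3.1.1 and 3.1.2 of all three SAPs, replace the set-to-missing rule. When a reaction is not known to have resolved, or is judged chronic, keep the time from onset to the last day it was known present as a lower bound, taken from the continued e-diary entries or the CRF. State that participants who leave while symptomatic during Days 1–7 are treated the same way, which removes the two readings.

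In Section 6.1.1.2:
- report per group, for each reaction, the number unresolved, chronic or without an end date;
- show the maximum as ≥x days where the longest reaction is unresolved;
- add a supplementary mean using the lower bounds, labelled as a minimum.

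A Kaplan-Meier median is optional and would probably add little.

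The cost is SAP wording and minor programming, and reported durations become slightly longer. No new collection should be needed, with one caveat: the documents describe CRF entry of end dates, not of a last-known-present date. Where the CRF and later diary entries are silent, the last diary day with the reaction serves as the lower bound.

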3.1.2. Systemic Events

The systemic events assessed and recorded in the e-diary are fever, fatigue, headache, chills, vomiting, diarrhea, new or worsened muscle pain, and new or worsened joint pain from Day 1 through Day 7, where Day 1 is the day of vaccination.

If a systemic event persists beyond the end of the 7-day e-diary collection period following vaccination, the participant will be requested to report that information and the corresponding resolution date. The investigator will enter this resolution date on the Summary of Reactogenicity CRF page.

The systemic events collected on the Participant Reported Reactogenicity CRF page will be combined with the 7-day e-diary data and included for the below analysis (presence, maximum severity, onset day, and duration).

The derivations for systemic events will be handled similarly to the way local reactions are handled for presence of the event, severity level, duration, and onset day.

The variables associated with the systemic events will be computed similarly to the way local reactions are computed (see [Section 3.1.1](#)).

1. Presence (yes or no) of each systemic event on each day (Day 1 through Day 7) after vaccination.

2. Presence (yes or no) of each systemic event on any day (Day 1 through Day 7) after vaccination.
3. Presence or absence of each severe/Grade 4 systemic event on each day and any day (Day 1 through Day 7) after vaccination.
4. Maximum severity of each systemic event on any day (Day 1 through Day 7) after vaccination.
5. Presence or absence of any systemic event on any day (Day 1 through Day 7) after vaccination.
6. Duration of each systemic event after vaccination.
7. Onset day of each systemic event after vaccination.
8. Onset day of any systemic event after vaccination.

The symptoms will be assessed by the participant as absent, mild, moderate, or severe according to the grading scale in Table 6.

Table 6. Systemic Event Grading Scale

	Mild (Grade 1)	Moderate (Grade 2)	Severe (Grade 3)	Potentially Life-Threatening (Grade 4^a)
Vomiting	1-2 times in 24 hours	>2 times in 24 hours	Requires IV hydration	Emergency room visit or hospitalization for hypotensive shock
Diarrhea	2 to 3 loose stools in 24 hours	4 to 5 loose stools in 24 hours	6 or more loose stools in 24 hours	Emergency room visit or hospitalization for severe diarrhea
Headache	Does not interfere with activity	Some interference with activity	Prevents daily routine activity	Emergency room visit or hospitalization for severe headache
Fatigue/tiredness	Does not interfere with activity	Some interference with activity	Prevents daily routine activity	Emergency room visit or hospitalization for severe fatigue
Chills	Does not interfere with activity	Some interference with activity	Prevents daily routine activity	Emergency room visit or hospitalization for severe chills
New or worsened muscle pain	Does not interfere with activity	Some interference with activity	Prevents daily routine activity	Emergency room visit or hospitalization for severe new or worsened muscle pain

Table 6. Systemic Event Grading Scale

	Mild (Grade 1)	Moderate (Grade 2)	Severe (Grade 3)	Potentially Life-Threatening (Grade 4^a)
New or worsened joint pain	Does not interfere with activity	Some interference with activity	Prevents daily routine activity	Emergency room visit or hospitalization for severe new or worsened joint pain

- a. Only an investigator or qualified designee is able to classify a participant's systemic event as Grade 4, after clinical evaluation of the participant or documentation from another medically qualified source (eg, emergency room or hospital record) or telephone contact with the participant. A Grade 4 event that meets the definition of an SAE will be collected on the AE CRF.

To record information on fever, a thermometer will be given to participants with instructions on how to measure oral temperature at home. Temperature will be collected in the reactogenicity e-diary each evening during the reactogenicity e-diary reporting period. It will also be collected at any time during the reactogenicity e-diary data collection period, or longer following vaccination, when fever is suspected.

Fever is defined as an oral temperature $\geq 38.0^{\circ}\text{C}$ ($\geq 100.4^{\circ}\text{F}$). The highest temperature for each day will be recorded in the reactogenicity e-diary. Temperature will be measured and recorded to 1 decimal place. Temperatures recorded in degrees Fahrenheit will be programmatically converted to degrees Celsius and then categorized according to the scale shown in Table 7 during analysis.

Table 7. Scale for Fever

$\geq 38.0\text{-}38.4^{\circ}\text{C}$ ($100.4\text{-}101.1^{\circ}\text{F}$)
$>38.4\text{-}38.9^{\circ}\text{C}$ ($101.2\text{-}102.0^{\circ}\text{F}$)
$>38.9\text{-}40.0^{\circ}\text{C}$ ($102.1\text{-}104.0^{\circ}\text{F}$)
$>40.0^{\circ}\text{C}$ ($>104.0^{\circ}\text{F}$)

